Various biologic therapies that target specific immunological pathways have been studied as potential therapeutics for UC. Experimental studies suggest that blocking the interleukin-23 (IL-23)/T helper 17/interleukin-17 immune axis alone is effective to treat inflammation in UC (Monteleone et al. 2009). Agents specifically targeting the IL-23 p19 subunit, including LY3074828, are in development for many autoinflammatory diseases to determine whether improvement in efficacy can be achieved by targeting IL-23 specifically (Gaffen et al. 2014).

LY3074828 is a humanized immunoglobulin G4–variant monoclonal antibody (molecular weight approximately 144,000 Da) that is directed against the p19 subunit of IL-23 and does not bind interleukin-12.

Eli Lilly has an ongoing (database locked, clinical study report pending) Phase 1 (first-in-human) ascending-dose study in which 33 subjects with psoriasis and 5 healthy subjects have each been administered a single dose of LY3074828. No serious adverse events (SAEs) were reported, and no subject was discontinued because of an adverse event (AE).

This Phase 2 study will provide efficacy data on intravenous (IV) administration of LY3074828 (3 doses versus placebo) in subjects with moderate to severe UC.

Clinical Protocol Synopsis: Study I6T-MC-AMAC

Name of Investigational Product: LY3074828	
Title of Study: A Phase 2, Multicenter, Randomized, Double-Blind, Parallel, Placebo-Controlled Study of LY3074828 in Subjects with Moderate to Severe Ulcerative Colitis	
Number of Planned Subjects: Approximately 240 subjects will be randomized.	Phase of Development: Phase 2
Length of Study: Subject participation is up to 120 weeks Estimated first subject visit: November 2015 Estimated last subject visit: October 2019	

Objectives: The primary objective of this study is to test the hypothesis that treatment with LY3074828 is superior to placebo in inducing clinical remission at Week 12 in subjects with moderate to severe ulcerative colitis (UC).
 
The secondary objectives are:
 
 • To evaluate the safety and tolerability of treatment with LY3074828 • To evaluate the efficacy of treatment with LY3074828 in inducing a clinical response at Week 12 • To evaluate endoscopic remission at Week 12 and Week 52 • To evaluate the effect of maintenance treatment with LY3074828 on the durability of clinical remission, endoscopic remission, and clinical response at Week 52 • To evaluate the effect of LY3074828 on health outcomes/quality of life measures (Inflammatory Bowel Disease Questionnaire score, 36-Item Short Form Health Survey score, Patient's Global Impressions of Severity score, and Patient's Global Impressions of Improvement score) • To characterize the pharmacokinetic (PK) profile of LY3074828 	

Study Design: Study I6T-MC-AMAC is a multicenter, randomized, double-blind, parallel-arm, placebo-controlled trial in which approximately 240 subjects will be randomized. Subjects must have moderate or severe UC (defined as a Mayo score of 6 to 12 with an endoscopic subscore ≥ 2). Approximately two-thirds (~160) of the subjects randomized to study treatment must have been exposed to at least 1 previous biologic therapy (such as tumor necrosis factor antagonists, vedolizumab, or experimental UC biologic), and approximately one-third (~80) of the subjects will be naive to biologic therapy.
 
Screening Period: Subjects will be evaluated for study eligibility ≤ 28 days before the baseline visit. At the baseline visit, subjects who fulfill the eligibility criteria will be randomized equally to 1 of 4 induction treatment arms.
 
Induction Period: A 12-week induction period is designed to establish the efficacy and safety of LY3074828 administered IV at Weeks 0, 4, and 8. Subjects will be stratified across the treatment arms on the basis of previous exposure to biologic therapy for treatment of UC. Subjects who discontinue the study for any reason before the end of the induction period will complete the induction period early termination visit.
 
Maintenance Period: The maintenance period is designed to explore the safety and durability of clinical responses and remissions to treatment with 200-mg LY3074828 administered subcutaneously (SC) every 4 weeks (Q4W) or every 12 weeks (Q12W). Subjects defined as having clinical responses at Week 12 will continue study participation in the maintenance period up to Week 104. Subjects who do not meet clinical response criteria at Week 12 will have the option to continue in a study extension period or discontinue from the study. Responding subjects who have received LY3074828 in induction period will be re-randomized to 1 of 2 LY3074828 maintenance treatment arms (200 mg Q4W or 200 mg Q12W); these subjects will be stratified according to their Week-12 remission status. Any responding subjects in the placebo arm SC Q4W will remain on placebo. After Week 52, subjects who experience worsening of UC (partial Mayo score of 7 or more) may receive rescue treatment with LY3074828 200 mg SC Q4W. Subjects who discontinue the study for any reason during the maintenance period will complete the maintenance period early termination visit.
 
Maintenance Follow-Up Period: The follow-up period will include a visit every 4 weeks for a total of 16 weeks following Week 104 to assess subject safety. Subjects who discontinue the study for any reason during the maintenance follow-up period will complete the maintenance period early termination visit.
	

Extension Period: Subjects who complete the study induction period (through Visit 7) but do not have a clinical response may choose to participate in the unblinded study extension period following consultation with, and at the discretion of, the investigator. Subjects who discontinue the study for any reason during the extension period will complete the extension period early termination visit.

Extension Follow-Up Period: A follow-up period will include a visit every 4 weeks for a total of 16 weeks following Extension Week 92 to assess subject safety. Subjects who discontinue the study for any reason during the extension follow-up period will complete the extension period early termination visit.

Diagnosis and Main Criteria for Inclusion and Exclusions: This study will include male or female subjects ≥ 18 and ≤ 75 years of age with moderate to severe active UC (defined as a Mayo score of 6 to 12 with an endoscopic subscore ≥ 2).

Investigational Product, Dosage, and Mode of Administration or Intervention:

Induction Period:

50 mg, 200 mg, or 600 mg LY3074828 given as an IV infusion (Weeks 0, 4, 8)

The 50-mg and 200-mg arms will use exposure-based dosing: doses for individuals in the 50-mg and 200-mg arms may be increased at Weeks 4 and 8 if the projected trough concentrations of LY3074828 for those visits fall below prespecified thresholds. Dose level changes in these patients will be communicated to the site by the sponsor.

Maintenance Period:

Responding subjects (as defined by the protocol) will be re-randomized to receive 200 mg LY3074828 given SC either Q4W or Q12W.

Extension Period:

Nonresponding subjects (as defined by the protocol) may continue in the study and receive LY3074828.

Reference Therapy, Dose, and Mode of Administration or Comparative Intervention:

Induction Period: Placebo (0.9% normal saline) as an IV infusion (Weeks, 0, 4, 8)

Maintenance Period: Placebo given SC Q4W

Planned Duration of Treatment:

Induction period: 12 weeks

Maintenance period: 92 weeks

Extension period (for nonresponders): 92 weeks

Criteria for Evaluation:

Efficacy: The following efficacy measures will be assessed in this study: clinical remission at Week 12, clinical response at Week 12, and endoscopic remission at Week 12 and Week 52.

Safety: The following safety measures will be assessed in this study: AEs; SAEs; vital signs; electrocardiograms (ECGs); physical examinations; and laboratory safety evaluations including chemistry, hematology, and urinalysis.

Health Outcomes: The following health outcomes measures will be assessed in this study: Patient's Global Impressions of Severity score, Patient's Global Impressions of Improvement score, Inflammatory Bowel Disease Questionnaire score, and 36-Item Short Form Health Survey score.

Pharmacokinetic: Serum for the measurement of LY3074828 time-concentration profiles will be collected as specified in the visit schedule.

Statistical Methods:

Statistical: Approximately 240 subjects will be randomized to 1 of 4 double-blind treatment regimens: placebo, 50 mg LY3074828 exposure-based dosing, 200 mg LY3074828 exposure-based dosing, or the 600-mg LY3074828 fixed-dose treatment group in a 1:1:1:1 ratio (~60 subjects per arm). Approximately one-third are to be biologic-naive subjects (~20 per arm) and approximately two-thirds are to have been exposed to at least 1 previous biologic agent (~40 per arm).

Efficacy analyses will be conducted on the intent-to-treat population. Safety analyses will be conducted on the safety population. Subjects will be analyzed according to the treatment to which they were assigned.

All tests of treatment effects will be conducted at a 2-sided alpha level of 0.05 unless otherwise stated. Summary statistics for continuous variables may include mean, standard deviation, median, and minimum and maximum

values; categorical variables will be presented as counts and percentages.

Efficacy: The rates of remission and nonremission will be summarized by dose level and previous biologic use (yes/no). For categorical measures of efficacy, the differences between each treatment arm and placebo will be tested separately via a logistic regression model that controls for previous biologic use.

Safety: Safety will be assessed by evaluating all reported AEs and changes in laboratory analytes, ECGs, and vital signs (including body weight). Duration of exposure to therapy will be calculated for each subject and summarized by treatment group.

In the analysis of treatment-emergent adverse events (TEAEs) during the induction period, all preexisting conditions recorded at screening (Visit 1) and any on-study AEs recorded at or before dosing at baseline (Visit 2) will be used as baseline. The induction period and the maintenance period will be analyzed separately. For each event classification term, the number of subjects experiencing a TEAE with that classification term will be tabulated.

Additional safety parameters include laboratory test results, ECGs, and vital-sign measurements. The baseline for computing the change in safety variables for the induction period will be data collected at or before dosing on Visit 2; the baseline for the maintenance period will be the last value collected during the induction period. The parameters will be listed and summarized with standard descriptive statistics. Change from baseline will also be summarized by randomized treatment.

Health Outcomes: Mean change from baseline in health outcomes measures will be summarized by treatment group.

Pharmacokinetics/Pharmacodynamics:

Population PK analyses will be performed to characterize the PK of LY3074828 after IV and SC dosing. These analyses will include model-based and graphical evaluations of the data. Estimates of PK model parameters and covariate effects and corresponding 90% confidence intervals will be reported.

Population PK/PD analyses will be conducted to evaluate the relationship between LY3074828 concentrations and/or dose and clinical response as measured by the primary endpoint of clinical remission, Mayo subscores, and other biomarkers and endpoints.

3. Table of Contents

A Phase 2, Multicenter, Randomized, Double-Blind, Parallel, Placebo-Controlled Study of LY3074828 in Subjects with Moderate to Severe Ulcerative Colitis

Section	Page
1. Protocol I6T-MC-AMAC(c) A Phase 2, Multicenter, Randomized, Double-Blind, Parallel, Placebo-Controlled Study of LY3074828 in Subjects with Moderate to Severe Ulcerative Colitis	1
2. Synopsis	2
3. Table of Contents.....	6
4. Abbreviations and Definitions.....	12
5. Introduction	16
6. Objectives.....	20
6.1. Primary Objective	20
6.2. Secondary Objectives.....	20
6.3. Exploratory Objectives.....	20
7. Investigational Plan.....	21
7.1. Summary of Study Design.....	21
7.1.1. Study Extensions.....	23
7.2. Discussion of Design and Control	24
8. Study Population.....	26
8.1. Inclusion Criteria.....	26
8.2. Exclusion Criteria	28

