12.2. Statistical and Analytical Plans

12.2.1. General Considerations

Statistical analysis of this study will be the responsibility of Eli Lilly and Company or its designee.

The subject populations to be analyzed for this study are defined in [Table AMAC.4](#).

Table AMAC.4. Analysis Populations

Population	Definition
Screening	all subjects who signed informed consent and participated in the screening period (Visit 1)
Safety Population	all randomized patients who receive at least 1 dose of study treatment. maintenance period: only subjects who received LY3074828 during the induction phase, met the protocol definition of clinical response at Week 12, and then received any amount of investigational product in the maintenance phase
Intent-to-Treat (ITT)	all randomized patients, even if the patient does not take the assigned treatment, does not receive the correct treatment, or otherwise does not follow the protocol
PK-Evaluable	all subjects who received at least 1 dose of investigational product and have sufficient blood sampling to allow for PK evaluation

Efficacy analyses will be conducted on the intent-to-treat (ITT) population. Safety analyses will be conducted on the safety population. Subjects will be analyzed according to the treatment to which they were assigned, regardless of any errors of dosing.

All tests of treatment effects will be conducted at a 2-sided alpha level of 0.05 unless otherwise stated. Unless otherwise specified, no multiplicity adjustment will be considered for all planned analyses.

Summary statistics for continuous variables may include mean, standard deviation, median, and minimum and maximum values; categorical variables will be presented as counts and percentages.

Any change to the data analysis methods described in the protocol will require an amendment ONLY if it changes a principal feature of the protocol. Any other change to the data analysis methods described in the protocol and the justification for making the change will be described in the clinical study report. Additional exploratory analyses of the data will be conducted as deemed appropriate.

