12.2.8. Safety Analyses

Safety will be assessed by evaluating all reported AEs and changes in laboratory analytes, ECGs, and vital signs (including body weight).

Duration of exposure to therapy will be calculated for each subject and summarized by treatment group.

AEs will be coded according to the *Medical Dictionary for Regulatory Activities* and summarized by system organ class, preferred term, severity, and relationship to investigational product. A TEAE is defined as an event that first occurred or worsened in severity after baseline. In the analysis of TEAEs during the induction period, all preexisting conditions recorded at screening (Visit 1) and any on-study AEs recorded at or before baseline (Visit 2) will be used as baseline. In the analysis of TEAEs during the maintenance period, any on-study AEs recorded at Week 12 will be used as baseline. The induction period and the maintenance period will be analyzed separately. For each event classification term, the number of subjects experiencing a TEAE with that classification term will be tabulated. Treatment-related TEAEs are defined as events that are indicated by the investigator on the CRF to be related to treatment. If a subject reports the occurrence of a particular event more than once, the most severe of those events will be included in the summary tables of TEAEs, and the most severe of the most related of those events will be included in the summary tables of treatment-related events. TEAEs of interest will be presented.

Additional safety parameters include laboratory test results, ECGs, and vital-sign measurements. The baseline for computing the change in safety variables for the induction period will be data collected at or before dosing on Visit 2; the baseline for the maintenance period will be the last value collected during the induction period. The parameters will be listed and summarized with standard descriptive statistics. Change from baseline will also be summarized by randomized treatment.

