separately for the Induction Dosing Period and the Maintenance Dosing Period. Summaries and analyses will be also presented for the Extension Period.

By-patient listings will be sorted by treatment allocation, site and visit. Numeric data will be listed to the same number of decimal places as recorded on the eCRF. For derived variables, the number of decimal places will be listed as specified. The decimal points will be aligned in the data listings. For the tables and listings in the appendices, "Page x of X" will appear on each page.

By-patient listing will be generated for each SDTM dataset. If necessary, separate listing for derived variables (that are derived from the SDTM datasets) will be generated. Wherever applicable, listings will include the period of the study during which the event or measurement occurred.

Efficacy analyses will be conducted on the Intent-to-Treat (ITT) population. All safety analyses will be conducted on the Safety Population. These populations are defined in section 6.2.

Patients will be analyzed according to the treatment to which they were assigned regardless of any errors of dosing.

All tests of treatment effects will be conducted at a 2-sided alpha level of 0.05 unless otherwise stated. Unless otherwise specified, no multiplicity adjustment will be considered for planned analyses.

For all efficacy and health outcomes analyses, baseline is defined as the last non-missing assessment recorded on or prior to the date of first study drug injection at Week 0 (Visit 2). However, placebo patients who enter the Extension Period will have their baseline reset. Their new baseline will be defined as the last non-missing assessment on or prior to the date of first injection of study treatment at Week EW0 (Extension Visit 1).

Unless otherwise specified, variables will be analyzed in the original scale on which they are measured. However, if it is deemed more statistically appropriate, a transformation, such as to the logarithmic scale, may be applied before analysis. The parametric approach will be employed by default for statistical analysis except when nonparametric analysis, such as by a rank-based method, is assessed to be more fitting.

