6.2. Analysis Populations

The patient populations to be analyzed for this study are defined in the table presented below:

Table 2 Analysis Populations

Population	Definition
Screening	All patients who signed informed consent and participated in the screening period (Visit 1). This population will be used for the presentation of patient disposition.
Intent-to-Treat (ITT) Population	Efficacy and health outcome analyses will be conducted on the intent-to-treat population (ITT). The ITT population is defined as all randomized patients, even if the patient does not take the assigned treatment, does not receive the correct treatment, or otherwise does not follow the protocol. Patients will be analyzed according to the treatment to which they were assigned.
Safety Population	Safety analyses will be conducted on the Safety Population, defined as all randomized patients who receive at least one dose of study treatment. Patients will be analyzed according to the treatment to which they were assigned.

Induction Responders	A subset of the ITT population and will include those patients who are re-randomized to one of the two maintenance dosing period LY arms.
All enrolled in Extension Period	A subset of the ITT population and will include only the patients who participated in the Extension Period.

Analyses of the maintenance dosing period and the extension periods will be based on the corresponding enrolled population as described in the table above.

The Schedule of Events outlined in the protocol (attachment 1) specifies the allowable windows for assessments. A sensitivity analysis of the primary analysis may be conducted to investigate the exclusion of patients /assessments deemed to be major deviations from the protocol.

A Per-Protocol population may be evaluated in this study and patients to be excluded from that population will be identified through protocol deviations. All protocol exemptions and violations will be listed as described in section 9.10 of the protocol.

All statistical analyses will be performed using SAS software Version 9.2 (or a higher version). Visualizations tools such as Spotfire may also be used for dynamic displays.

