6.14. Safety Analyses

All safety evaluations will be based upon the Safety Population as defined in Section 6.2.

Any statistical comparisons for safety data will be performed only between the “All LY3074828” treatment group and Placebo. No pairwise comparisons between LY3074828 induction treatment arms will be performed. Pairwise comparison of LY3074828 maintenance treatment arms will be performed (no comparison to placebo). No multiplicity control procedure will be performed for these tests of safety data.

Safety and tolerability will be evaluated in terms of treatment-emergent AEs (TEAEs), AEs leading to permanent discontinuations of study drug, SAEs, deaths, changes in clinical laboratory test results, and vital signs. These measures will be analyzed for each dose group and combined LY3074828 groups, separately for each study part, as well as across study parts for key summaries.

For all quantitative safety analyses, baseline is defined as the last non-missing assessment recorded on or prior to the date of first study drug injection at Week 0 (Visit 2). However, placebo patients who enter the Extension Period will have their baseline reset. Their new baseline will be defined as the last non-missing assessment on or prior to the date of first injection of study treatment at Week EW0 (Extension Visit 1).

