Have chemistry: alanine aminotransferase (ALT) levels >2x upper limit of normal (ULN) at screening*	Programmable (clinical database)		May need to alter the ULN based on volume of subjects violating. LBTEST=' Alanine Aminotransferase'. Last lab collected on or before date of randomization will be utilized.

Have chemistry: aspartate aminotransferase (AST) levels >2x upper limit of normal (ULN) at screening*	Programmable (clinical database)		May need to alter the ULN based on volume of subjects violating. LBTEST=' Aspartate Aminotransferase'. Last lab collected on or before date of randomization will be utilized.
Have received cyclosporine or thalidomide ≤30 days of screening* for treatment of UC.	Programmable (clinical database)		Use Preferred name="CICLOSPORIN" or "TACROLIMUS" when ATC Codes L04AD or Preferred name="THALIDOMIDE" when ATC code=L04AX.
Have received corticosteroid enemas, corticosteroid suppositories or topical treatment with 5-ASA ≤30 days of screening* endoscopy for treatment of UC.	Non Programmable (Monitoring)		
Have used apheresis (Adacolumn apheresis) ≤2 weeks before screening* endoscopy for treatment of UC.	Programmable (clinical database)		Use Preferred name="MEDICAL DEVICES".
Have previous exposure to any biologic therapy for IL-23 (ustekinumab), either licensed or investigational.	Programmable (clinical database)		Preferred_Name='USTEKINU MAB'.
Have abdominal abscess or toxic megacolon during screening*	Non Programmable (Monitoring)		
Have positive hepatitis B surface antigen or positive anti-hepatitis B core antibody (HBcAb+) and positive confirmatory polymerase chain reaction (PCR) for HBV, regardless of anti-hepatitis B surface antibody status at screening*	Programmable (clinical database)		'Hepatitis B Virus Surface Antigen' 'Hepatitis B Virus Core Antibody'

Have positive result for hepatitis C antibody and positive confirmatory PCR test for hepatitis C virus at screening*	Programmable (clinical database)		'Hepatitis C Virus Antibody'
Had Clostridium difficile within 30 days of screening endoscopy or tests positive at screening*	Programmable (clinical database)		

* For definition of Baseline and Screening, Date of Randomization should be used for consistency throughout.

Category: Investigational Product			
Subcategory:			
Treatment Assignment/ Randomization Error			
Dosing Error	Non Programmable (Monitoring)	104 = Study drug not administered per protocol	

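### Safety is grouped by assigned treatment even after a dosing error, so events in a placebo subject given LY3074828 by mistake during induction count as placebo events, and the reverse

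*Protocol*

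**What the plan says.** Four places set the grouping rule, and all say assigned treatment.

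- **Protocol synopsis, Statistical Methods:** "Safety analyses will be conducted on the safety population. Subjects will be analyzed according to the treatment to which they were assigned".
- **Protocol 12.2.1**, just after naming the safety population: "Subjects will be analyzed according to the treatment to which they were assigned, regardless of any errors of dosing".
- **SAP 6.1**, again just after naming the Safety Population: "Patients will be analyzed according to the treatment to which they were assigned regardless of any errors of dosing".
- **SAP 6.2, Table 2, Safety Population row:** "Safety analyses will be conducted on the Safety Population, defined as all randomized patients who receive at least one dose of study treatment". The row ends: "Patients will be analyzed according to the treatment to which they were assigned".

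The rule then carries into the safety sections. SAP 6.14 says: "All safety evaluations will be based upon the Safety Population as defined in Section 6.2". Protocol 12.2.8, with the same sentence in the synopsis, says of laboratory, ECG and vital-sign data: "Change from baseline will also be summarized by randomized treatment".

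Dosing errors are recorded elsewhere. SAP 6.16, Table 9 has an Investigational Product category of important deviations. It includes treatment assignment error and dosing error, the latter identified as "Study drug not administered per protocol". Nothing there leads to regrouping for safety.

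**The concern.** Analysis by assignment preserves the randomised comparison, which is what ITT efficacy needs. A safety table is read as a statement about what happened to people exposed to the drug. Under the stated rule, having received a dose decides only whether a subject is in the Safety Population, not the column in which the subject is counted.

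Safety and tolerability is a secondary objective (Protocol 6.2). SAP Table 1 and SAP 6.14 limit the induction safety comparison to all LY3074828 against placebo, and the placebo side is one arm of about 60. A cross-over error between LY3074828 and placebo therefore goes straight into the one contrast that is tested, where the smaller group is sensitive to single subjects.

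The route to such an error is visible in the plan. Doses are prepared at sites by unblinded staff (Protocol 9.1), and individual doses can change at Weeks 4 and 8 (Protocol 9.5). The exposure summary would not necessarily show the error, because SAP 6.14.1.2 builds total dose from prescribed amounts and the injection schedule.

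**Working it through.** **Plan figure.** The plan gives no figure for this point. Its only design figure, 89% power for remission of 30% versus 7.5% with 60 per arm, reproduces as 89.4% (pooled chi-square) and has no bearing here.

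**Is there an exception to the rule?** Protocol 12.2.1 and SAP 6.1 set dosing errors aside explicitly. The synopsis and SAP Table 2 say as assigned and are silent on errors. SAP 6.14 inherits the Table 2 population. A few displays use wording based on drug received: the ordering of hypersensitivity and injection-site terms, the summary of events by antibody status, and the ALT/bilirubin plot that joins treatments when more than one was taken. None of these changes the general rule or the adverse event tables. SAP 6.14.1.1 and 6.14.1.2 keep subjects with dose modification in the randomised arm, which fits planned exposure-based increases because those are part of the assigned 50-mg and 200-mg regimens.

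**Inputs.** 1:1:1:1 allocation with 60 per arm (Protocol 12.1) gives 60 placebo and 3 × 60 = 180 LY3074828. The number misdosed and the event rates are assumptions.

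**Weight of one subject.** 1/60 = 1.7 percentage points of the placebo rate; 1/180 = 0.6 points of the LY3074828 total.

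**Expected attenuation.** Let m subjects in each direction receive the wrong treatment throughout, unrelated to event risk, with true event rates p1 on LY3074828 and p0 on placebo.

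- Placebo column: p0 + (m/60)(p1 − p0)
- LY3074828 column: p1 − (m/180)(p1 − p0)
- Difference: (p1 − p0)(1 − m/60 − m/180)

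| m each way | Factor | Difference if true rates are 15% vs 5% |
|---|---|---|
| 0 | 1.000 | 10.0 points |
| 1 | 0.978 | 9.8 |
| 2 | 0.956 | 9.6 |
| 3 | 0.933 | 9.3 |
| 6 | 0.867 | 8.7 |

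**One rare serious event.** Suppose a placebo-assigned subject is given LY3074828 from the first infusion and has the only drug-caused serious reaction.

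| Grouping | LY3074828 | Placebo | Exact two-sided 95% upper bound on LY3074828 |
|---|---|---|---|
| As assigned | 0/180 | 1/60 (1.7%) | about 2.0% |
| As received | 1/181 (0.6%) | 0/59 | about 3.0% |

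The direction of the observed difference reverses. Neither table supports an inference: Fisher's exact p is 60/240 = 0.25 for the first and 1.0 for the second. The harm is in description and attribution, not in a changed significance test.

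**The case against.** The best reply is that the issue is conditional and probably small, and that a serious case would not be hidden. SAP 6.14.2 requires a narrative for every death, serious adverse event and event leading to drug discontinuation. SAP 6.1 provides by-patient listings, SAP 6.16 lists violations needing medical review, and both documents allow further exploratory analyses. Table 9 is also a general catalogue that includes consent and ethics-approval lapses, so its dosing-error row does not show that such errors are likely.

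Much of this stands. A reader would be wrong to infer that the documents expect or report cross-arm misdosing; they give no rate. But narratives and listings do not move anyone between columns. The adverse event tables and the safety tests would still count the event in the wrong group.

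Three stronger readings also go too far.

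- **That misattribution always pulls the contrast towards no difference.** This holds only in expectation, with misdosing unrelated to event risk. The single-event example passes the null and reverses the sign.
- **That any dosing mix-up matters for the tested contrast.** A swap between LY3074828 dose arms leaves LY3074828 total versus placebo unchanged and affects only by-dose summaries.
- **That any LY3074828 dose in a period should reclassify the subject for the whole period.** Protocol 7.1 and SAP 5.1 permit LY3074828 rescue after Week 52. Such a rule would move a rescued placebo subject's earlier maintenance events to LY3074828, creating a new misattribution.

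**Conclusion.** The point holds as a defect in a stated rule, not as an omission. Protocol 12.2.1 and SAP 6.1 direct safety to be analysed as assigned whatever dosing errors occur, the synopsis and SAP Table 2 agree on assignment, and nothing offsets them.

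The effect is zero if no subject crosses between LY3074828 and placebo. If a few do, common events are little affected: one subject each way keeps 97.8% of the expected difference and six each way keep 86.7%, assuming wrong treatment throughout and no link with event risk. The practical exposure is a rare serious event, where one subject is 1.7 points of the placebo rate and can decide which column shows it. The change is worth making because it is cheap and removes a known bias, not because the documents show that misdosing happened.

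**What to change.** Keep assigned treatment for ITT efficacy. Group the induction Safety Population by treatment actually received:

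- A placebo-assigned subject given LY3074828 in error counts as LY3074828 from the first such dose. Earlier events stay under placebo.
- An LY3074828-assigned subject counts as placebo only if no LY3074828 was received in the period.
- Planned exposure-based increases stay in the randomised arm.
- Protocol-permitted rescue after Week 52 is not a dosing error and triggers no regrouping.

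If the error comes after Week 0, the subject has time in both columns, so the denominators need a footnote (for example 181 and 60, not 181 and 59). The plan should also say which dose column such a subject joins; the LY3074828 total does not depend on that choice.

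Amend six places together, so that no sentence contradicts the new rule: the synopsis population sentence, the synopsis sentence on safety change from baseline, Protocol 12.2.1, Protocol 12.2.8, SAP 6.1, and the Safety Population row of SAP Table 2. Footnote every reclassified subject and keep the as-assigned tables as a sensitivity analysis. SAP section 3 records that version 3 was approved after unblinding, so the change and its date should be documented.

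The cost is one derived actual-treatment variable, the wording edits and the footnotes. The small downside is that a few subjects may leave their randomised group, in the safety tables only.
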